3.13 CRITERIA FOR REMOVAL FROM PROTOCOL THERAPY AND OFF STUDY CRITERIA

Prior to documenting removal from protocol therapy, effort must be made to have all subjects complete a safety visit approximately 30 days following the last dose of study therapy.

3.13.1 Criteria for removal from protocol therapy

- Inability to undergo HIPEC
- Unwilling to comply with treatment regimen or prescribed follow-up
- Completion of treatment phase
- Positive pregnancy test

3.13.2 Off Study Criteria

- Death
- Disease progression requiring systemic therapy
- Start of any therapeutic agent other than mitotane
- Completed study follow-up period
- Participant requests to be withdrawn from the study
- Lost to follow up
- PI decision to close the study

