1 INTRODUCTION

1.1 STUDY OBJECTIVES

1.1.1 Primary Objective

- To determine intraperitoneal progression free survival after optimal debulking and heated intraperitoneal chemotherapy with cisplatin in patients with intraperitoneal spread of adrenocortical cancer

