1.1.2 Secondary Objectives

- Determine morbidity of this procedure in this patient population
- Determine the impact of surgery and HIPEC on QOL
- Determine the impact of surgery and HIPEC on hormone excess
- Examine patterns of recurrence (local versus systemic)
- Perform molecular analyses to try to discern if there are intrinsic differences between tumors that recur widely throughout the peritoneal surface and those that metastasize to other organs or are confined to a local recurrence.
- Determine overall survival after optimal debulking and heated intraperitoneal chemotherapy with cisplatin in patients with intraperitoneal spread of adrenocortical cancer.

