2 ELIGIBILITY ASSESSMENT AND ENROLLMENT

2.1 ELIGIBILITY CRITERIA

2.1.1 Inclusion Criteria

- Histologically proven ACC with the majority of disease confined to the peritoneal cavity and resectable or amenable to radiofrequency ablation
- Disease evaluable by CT or PET imaging
- All disease should be deemed resectable based on imaging studies e.g.:
 - Hepatic metastases (unilateral or bilateral ≤ 5 lesions, ≤ 15 cm total diameter)
 - **Note:** Hepatic lesions must be amenable to complete resection
 - Primary peritoneal metastases (small disease load $\leq P2$ disease) without massive ascites or intestinal obstruction
 - Lung metastases (≤ 3 unilateral/bilateral, 9 cm total diameter)
 - **Note:** lung lesions must be amenable to complete resection
 - **Note:** Patients with both pulmonary and hepatic metastases will be enrolled at the discretion of the PI
 - **Note:** In situations where resection to Completeness of Cytoreduction Score (CC) 0 or 1 is uncertain, patients may undergo diagnostic laparoscopy prior to enrollment to determine feasibility of resection. (**Appendix D**)
- Greater than or equal to 18 years of age
- Able to understand and sign the Informed Consent Document

- Clinical performance status of ECOG ≤ 2
- Life expectancy of greater than three months
- Patients of both genders must be willing to practice birth control during and for four months after receiving chemotherapy
- Hematology:
 - Absolute neutrophil count greater than 1500/mm³ without the support of Filgrastim.
 - Platelet count greater than 75,000/mm³.
 - Hemoglobin greater than 8.0 g/dl.
- Chemistry:
 - Serum creatinine less than or equal to 1.5 mg/dl unless the measured creatinine clearance is greater than 60 mL/min/1.73 m²
 - serum AST and ALT within 5 times the upper limit of normal and a total serum bilirubin of less than 3 times the upper limit of normal, both of which define the upper limit of grade 2 treatment related toxicities.
 - PT within 2 seconds of the upper limit of normal (INR \leq 1.8)
- Recovered from any toxicity to grade 2 or less from all prior chemotherapy, immunotherapy or radiotherapy and be at least 30 days past the date of their last treatment with the exception of mitotane which may be continued.
- Able to understand their disease and the exploratory nature of combining surgery and HIPEC for this histology.

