3.11 TREATMENT ASSESSMENT AND RESPONSE (FOLLOW UP PERIOD)

- Because of the nature of peritoneal imaging and because cytoreductive surgery will likely eliminate all imageable disease, response can only be measured in terms of radiographic disease-free survival. At any time point when there is evidence of progressive disease (imageable tumor nodules or increasing ascites persistent on CT scans as interpreted by the official interpretation of the imaging studies) the patients will be scored as progressive disease. In some cases this may require successive scans, but the time of

recurrence will be retrospectively defined at the point the first scan demonstrated imageable disease.

- Patients will be evaluated 3 months from the operative date (+/- 1 month) intervals for the first year; every four months for (+/- 1 month) the next year and then q 6 months (+/- 1 month) thereafter.
- The following evaluations will be performed at each visit:
 - Imaging studies
 - Physical examination to include ECOG, weight and vital signs
 - Tumor markers as indicated
 - CBC, acute care, mineral and hepatic panel, CRP, Albumin, pre-albumin, ferritin, Hgb A1c if elevated pre-op.
 - Completion of Health related Quality of Life Forms (HRQOL) – at the first follow up visit and then at each evaluation until off study.
- Patients who are unwilling or unable to return for follow up evaluation will be followed every 6 months by phone contact until off study criteria are met. The following information may be obtained:
 - Summary of treatment received since the previous contact
 - Estimation of ECOG status
 - Request for imaging studies, physical exam and laboratory reports to be sent to the PI

Note: if patient is taken off study prior to 1 year following surgery, the HRQOL will be completed at the off study evaluation if possible.

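### The off-study criteria can end intraperitoneal follow-up before any intraperitoneal progression, and section 8 does not say how such patients enter the analysis of the primary endpoint

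*Combined protocol and SAP*

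**What the plan says.** Section 1.1.1 sets a site-specific primary objective: "To determine intraperitoneal progression free survival after optimal debulking and heated intraperitoneal chemotherapy with cisplatin".

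Section 3.13.2 lists the off-study criteria. Two matter here, and neither names a site: "Disease progression requiring systemic therapy" and "Start of any therapeutic agent other than mitotane". The second does not require progression.

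Section 3.11 attaches imaging to the follow-up visits: "Patients will be evaluated 3 months from the operative date (+/- 1 month) intervals for the first year", then every four months for a year, then every six. Patients who cannot or will not return "will be followed every 6 months by phone contact until off study criteria are met", and the request for outside imaging reports is part of that contact. Section 3.11 scores as progression "progressive disease (imageable tumor nodules or increasing ascites persistent on CT scans as interpreted by the official interpretation of the imaging studies", again without naming a site.

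Extraperitoneal disease is foreseen. Section 2.1.1 admits "Lung metastases (≤ 3 unilateral/bilateral, 9 cm total diameter", section 2.4 makes visceral metastatic disease a stratum, and section 1.1.2 includes the objective "Examine patterns of recurrence (local versus systemic".

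Section 8 plans 24 evaluable patients, 80% power for a median PFS of 10 rather than 5 months at one-sided 0.10, and Kaplan-Meier curves with confidence intervals. It does not say what happens to a patient with extraperitoneal progression, new therapy or death.

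**The concern.** The endpoint is tied to one site, but the end of observation is not. Take a patient whose lung disease progresses, whose peritoneum is clear, and who starts chemotherapy. That patient meets an off-study criterion. No later scan, report request or death collection is described, so a later peritoneal progression would go unrecorded. A patient who starts a new agent without imaged progression is lost in the same way.

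With 24 patients, a handful of such losses can move the estimated median. The plan also leaves open whether each loss is an event, a censoring or a competing risk, and that choice decides the direction of the error. The same gap affects overall survival, a secondary objective. It also hides peritoneal recurrences that follow a first systemic one.

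**Working it through.** **1. The plan's own figure.** Under an exponential 10-month median, S(5) = 2^(−5/10) = 0.7071; under the null it is 0.5. With n = 24 and z = 1.2816,

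power = Φ[((0.7071 − 0.5)·√24 − 1.2816·0.5) / √(0.7071·0.2929)] = Φ[(1.0146 − 0.6408)/0.4551] = Φ(0.82) = 79.4%.

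The stated 80% reproduces. It assumes that no intraperitoneal follow-up is lost.

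**2. If these patients are censored.** The documents give neither the extraperitoneal rate nor its correlation with peritoneal progression, so both are assumed. Let the two times share a gamma frailty with mean 1 and variance v. Let r be the ratio of the rescue or extraperitoneal hazard to the intraperitoneal hazard. The fraction censored before an intraperitoneal event is r/(1 + r). The Kaplan-Meier curve then converges to [1 + vλ(1 + r)t]^(−1/(v(1 + r))), where λ is the baseline intraperitoneal hazard, and its median is

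true median × (2^(v(1 + r)) − 1) / [(1 + r)(2^v − 1)].

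For a true median of 7 months:

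| r | censored first | v = 0 | v = 0.5 | v = 1.0 |
|---|---|---|---|---|
| 0.25 | 20% | 7.0 | 7.3 | 7.7 |
| 0.5 | 33% | 7.0 | 7.7 | 8.5 |
| 1.0 | 50% | 7.0 | 8.4 | 10.5 |

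Example, v = 1 and r = 1: 7 × (2² − 1)/(2 × 1) = 10.5. Kendall's tau is v/(v + 2), so these variances correspond to tau of 0.20 and 0.33.

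**3. Effect on the planned comparison with 5 months.** A separate simulation used 24 patients, 6,000 runs per scenario, exponential margins linked by a gamma frailty, no deaths, and rejection when (S(5) − 0.5)/Greenwood SE exceeds 1.2816. The true intraperitoneal median is 5 months, so every rejection is false.

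| tau | extraperitoneal median (months) | censored first | Kaplan-Meier median (months) | false positives |
|---|---|---|---|---|
| 0 | 5 / 10 / 20 | 50 / 33 / 20% | 5.0 / 5.0 / 5.0 | 12 / 11 / 11% |
| 0.3 | 5 / 10 / 20 | 50 / 27 / 13% | 6.4 / 5.6 / 5.3 | 28 / 19 / 14% |
| 0.5 | 5 / 10 / 20 | 50 / 20 / 9% | 7.7 / 5.9 / 5.4 | 41 / 23 / 16% |

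With intraperitoneal follow-up kept complete, the same test rejects in 7% to 8% of runs.

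**4. If extraperitoneal progression is an event.** In the model of step 2, any-site survival is [1 + vλ(1 + r)t]^(−1/v), so its median is the true intraperitoneal median divided by (1 + r), whatever v is. A true 7 months reads as 7/1.25 = 5.6, 7/1.5 = 4.7 or 7/2 = 3.5 months. In the simulation, with a true intraperitoneal median of 10 months and an extraperitoneal median of 10 to 40, the any-site median is 5.0 to 9.3 months. Power is 8% to 63%, against 74% to 76% with complete intraperitoneal follow-up.

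**The case against.** The strongest reply is that the plan never says these patients are censored. This stands. A reader might infer censoring from the Kaplan-Meier curves of section 8, but no rule is written. The progression definition in 3.11 names no site, and the 5.0-month comparator is plain PFS. On that reading a lung progression is an event and the error runs the other way. A one-directional claim of upward bias is therefore not supported.

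A reader might also infer that every lung or liver progression ends follow-up. It does not. The criterion requires progression that needs systemic therapy, so progression managed without it, or with mitotane alone, stays on study. Section 1.2.5 says metastasectomy is used extensively at this institution, so that group may not be small. Nor do the documents settle whether a liver recurrence is extraperitoneal: section 3.4 treats liver metastases as intra-abdominal.

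It is tempting to say that the patients lost are those with the most aggressive disease. That is plausible but undocumented, and without correlation the bias in the median is zero.

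The 10.5-month figure is the extreme cell: it needs variance 1.0 and half the patients censored first, in a population selected for mainly peritoneal disease. The other five cells with frailty shift the median by 0.3 to 1.5 months. For scale, with 24 uncensored patients and an exponential 7-month median, the standard error of the median is (0.5/√24)/(0.5·ln 2/7) ≈ 2.1 months. The cell also does not show that a 7-month treatment would wrongly pass, because the planned test is against 5 months. Step 3 is the relevant check.

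Finally, site of first recurrence may suffice for the recurrence-pattern objective. That is fair, so the secondary objective adds little weight.

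None of this restores the missing observations. A new agent started without progression loses intraperitoneal status under either reading.

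**Conclusion.** The point holds in a limited form. The off-study criteria can stop measurement of the primary endpoint in foreseeable patients, and section 8 does not say how they are analysed. That scans stop is implied by off-study status and by the absence of any later follow-up; it is not stated outright.

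The direction of bias depends on the unwritten rule. Under censoring with positive correlation, a true 7-month median reads as 7.3 to 10.5 months. At a true 5 months, the false-positive rate is 14% to 41% for tau of 0.3 to 0.5, against a nominal 10%. Without correlation the median is unbiased and the rate is 11% to 12%. Under any-site scoring, intraperitoneal PFS is understated and power falls. All of these sizes rest on assumed correlations and extraperitoneal rates. A reader should not infer that the sample size is wrong: the stated power reproduces. The change should be made, because intraperitoneal data not collected after a patient leaves may be impossible to recover.

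**What to change.** In 3.13.2, separate the end of protocol visits from the end of endpoint follow-up. After either trigger, keep collecting routine-care abdominal/pelvic CT reports, by the report-request route already in 3.11, together with deaths, until first intraperitoneal progression or death, whatever later therapy is given. This requires no extra scans and leaves treatment unchanged.

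In section 8:

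- State that the event is intraperitoneal progression or death. Record the site of each progression, and say whether liver counts as intraperitoneal.
- State how extraperitoneal progression and new therapy are handled in the primary analysis. This is a choice of estimand for the sponsor, and continued collection is worthwhile whichever is chosen.
- Add three sensitivity analyses: start of a new anticancer agent counted as an event; any-site PFS; and the cumulative incidence of intraperitoneal progression with competing risks.

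The cost is an amendment to both sections, some added record collection, and a few short analyses. Outside scans will be off schedule and may come from other centres. Later intraperitoneal status will partly reflect subsequent therapy, which could itself delay peritoneal progression; counting a new agent as an event shows how much the result depends on that.

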3.13.3 Off Protocol Therapy and Off Study Procedure

Authorized staff must notify Central Registration Office (CRO) when a subject is taken off protocol therapy and when a subject is taken off-study. A Participant Status Updates Form from the web site (<http://home.ccr.cancer.gov/intra/eligibility/welcome.htm>) main page must be completed and sent via encrypted email to: NCI Central Registration Office [contact].

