6.3.2 Exclusions to Routine Adverse Event Reporting

The following Adverse Events will be captured only in the source documents and will not be reported in C3D.

- For the duration of the study
 - Laboratory values that do not support the diagnosis of a reportable event with the exception of noted events in section 6.3.2.
 - All grade 1 events
- During hospitalization for surgical resection
 - Grade 1 and 2 events
 - Grade 3 and 4 events which resolve during the first 72 hours following surgery
- Post-operative recovery phase (following discharge)
 - Grade 1 and 2 events
 - Events that result in a hospitalization for convenience will not be reported.
- During the follow up period (more than 30 days following the last treatment)
 - Only those events that are serious, unexpected, and related to the treatment will be captured in C3D.

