7.2 NCI-IRB AND CLINICAL DIRECTOR REPORTING

7.2.1 NCI-IRB and NCI CD Expedited Reporting of Unanticipated Problems and Deaths

The Protocol PI will report in the NIH Problem Form to the NCI-IRB and NCI Clinical Director:

- All deaths, except deaths due to progressive disease
- All Protocol Deviations
- All Unanticipated Problems
- All non-compliance

Reports must be received within 7 days of PI awareness via iRIS.

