7.2.2 NCI-IRB Requirements for PI Reporting at Continuing Review

The protocol PI will report to the NCI-IRB:

1. A summary of all protocol deviations in a tabular format to include the date the deviation occurred, a brief description of the deviation and any corrective action.
2. A summary of any instances of non-compliance

3. A tabular summary of the following adverse events:
 - All Grade 2 unexpected events that are possibly, probably or definitely related to the research;
 - All Grade 3 and 4 events that are possibly, probably or definitely related to the research;
 - All Grade 5 events regardless of attribution;
 - All Serious Events regardless of attribution.

NOTE: Grade 1 events are not required to be reported

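### Overall survival is a secondary objective, but patients leave the study at progression needing systemic therapy or at a new agent, and the plan sets no later survival follow-up and no censoring rule

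*Combined protocol and SAP*

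**What the plan says.** - **Objective.** Section 1.1.2 lists, among the secondary objectives, "Determine overall survival after optimal debulking and heated intraperitoneal chemotherapy with cisplatin" in this population.
- **Exit.** Section 3.13.2 ends study participation at "Disease progression requiring systemic therapy" and at "Start of any therapeutic agent other than mitotane". Death, withdrawal, loss to follow-up and completion of the follow-up period are also listed. The length of that period is not given.
- **Two statuses.** Section 3.13.1 lists removal from protocol therapy separately. Section 3.13.3 requires notice to the registration office "when a subject is taken off protocol therapy and when a subject is taken off-study". So being off study is not the same as being off treatment and still followed.
- **Remote contact.** Under section 3.11, patients who cannot or will not return "will be followed every 6 months by phone contact until off study criteria are met".
- **Safety routes to deaths.** In the follow-up period, section 6.3.2 says: "Only those events that are serious, unexpected, and related to the treatment will be captured in C3D". The expedited list in section 7.2.1 covers "All deaths, except deaths due to progressive disease". The continuing-review table in section 7.2.2 includes "All Grade 5 events regardless of attribution".
- **Analysis.** Section 8 covers median PFS. Kaplan-Meier is the only time-to-event estimate it names. It gives no OS time origin, event definition or censoring rule.

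**The concern.** An OS estimate needs deaths to be sought in everyone, including patients who have progressed and moved to other treatment. Here the two exit criteria remove some of those patients at a moment tied to prognosis, and the plan has no procedure for learning what happens to them next. If the analyst censors them at exit, which is the natural default when no later data exist, the independent-censoring assumption of Kaplan-Meier fails.

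The protocol gives longer OS as part of its rationale (section 1.2.1) and of the potential benefit (section 9.4), so readers will look at this curve. Exits of this kind are foreseeable, since section 9.5 says the team can often arrange further treatment after recurrence.

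**Working it through.** **1. The plan's own figure.** There is none for OS. The primary figure is 80% power for a median PFS of 10 against 5 months, with n = 24 and one-sided alpha 0.10. Treat it as a one-sample test of S(5) = 0.5, with S(5) = 0.5^(5/10) = 0.707 under the alternative:

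Power = Φ{[(0.707 − 0.5)√24 − 1.2816 × 0.5] / √(0.707 × 0.293)} = Φ(0.82) = 79.4%.

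The stated 80% is reproduced, and nothing below enters that calculation.

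**2. Can a death after exit reach the data?**

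| Route | After exit |
|---|---|
| Clinic visits and phone contact (3.11) | Visits are study evaluations; phone contact ends at off-study |
| Death as an off-study event (3.13.2, 3.13.3) | Reaches only patients still on study |
| Database capture in follow-up (6.3.2) | Serious, unexpected and related events only |
| Expedited reports (7.2.1) | Deaths from progressive disease left out |
| Continuing-review table (7.2.2) | Fatal events listed, but no procedure to find them after exit |

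This step needs no assumed number.

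**3. Inputs for the size.** From section 8: median 10 months to first event (the PFS target), 24 patients and 60 months of accrual. Assumed, because the documents do not give them:
- 5% early deaths, uniform over months 0-2
- a share d = 0-20% of the other first events are deaths without progression
- median survival after progression 6-20.8 months
- a share s = 30-70% of progressors exit at progression
- for counting deaths, administrative censoring at 12-72 months

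The averages of 14 and 30 months in section 1.2.1 are survival after systemic chemotherapy in 14 retrospective patients. They are not survival after progression on this trial and are not used as such.

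**4. Formulas.** Let λ1 = ln2/10, and let λL and λS be the death hazards after progression of leavers and stayers. Put A(t) = exp(−λ1·t) and Gx(t) = [λ1/(λx − λ1)] × [A(t) − exp(−λx·t)]. After month 2:

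- True OS(t) = 0.95 × {A + (1 − d)[s·GL + (1 − s)·GS]}.
- Death hazard seen with censoring at exit = [d·λ1·A + (1 − d)(1 − s)·λS·GS] / [A + (1 − d)(1 − s)·GS].

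If λL = λS and both exceed d·λ1, exit takes higher-hazard patients out of the risk set and the curve is too high. If leavers do much better than stayers, exit takes out the patients who would have lowered the average hazard, and the error can vanish or reverse.

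Check with d = 0 and both post-progression medians 6 months: A(24) = 0.1895, G = 1.5 × (0.1895 − 0.0625) = 0.1905, OS = 0.95 × 0.380 = 36.1%. Simulation (600,000 patients per cell) gave 36.0%.

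**5. Leavers and stayers alike.** Error in 24-month OS, in points, for post-progression medians of 6 / 9.7 / 14 / 20.8 months:

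| d | True OS (%) | 30% exit | 50% exit | 70% exit |
|---|---|---|---|---|
| 0% | 36.0 / 47.1 / 56.3 / 65.5 | 8.0 / 6.4 / 5.2 / 3.8 | 15.8 / 12.6 / 10.3 / 7.7 | 27.2 / 21.8 / 17.4 / 13.2 |
| 10% | 34.2 / 44.2 / 52.4 / 60.7 | 6.8 / 5.3 / 4.0 / 3.0 | 13.2 / 10.4 / 7.9 / 5.6 | 22.2 / 17.3 / 13.3 / 9.2 |
| 20% | not tabulated | 5.5 / 4.2 / 3.0 / 2.0 | 10.7 / 8.0 / 5.8 / 3.6 | 17.9 / 13.4 / 9.8 / 5.9 |

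**6. Selective exit.** Same model, d = 0-20%, with different assumed medians for leavers and stayers:

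| Leavers / stayers (months) | 30% exit | 50% exit | 70% exit |
|---|---|---|---|
| 14 / 4 | 0.0 to +0.7 | +1.9 to +4.1 | +6.0 to +11.8 |
| 20.8 / 4 | about −2 | −1.8 to −0.5 | +0.8 to +5.2 |

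With leavers at 6 and stayers at 14 months, the error runs from about +8 to about +31 across these exit shares.

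**7. Deaths and precision.** Leavers and stayers alike, d = 0-10%, n = 24:

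| Exit share | Deaths observed | Standard error of 24-month OS (points) |
|---|---|---|
| None (full follow-up) | 13.4-19.6 | 10.1-10.6 |
| 30% | 9.8-14.7 | 11.0-12.3 |
| 50% | 7.3-11.4 | 11.4-13.8 |
| 70% | 4.9-8.2 | 11.9-14.9 |

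**8. No-bias check.** With a constant death hazard and an assumed median OS of 18 months, true 24-month OS is 0.5^(24/18) = 39.7%. Censored Kaplan-Meier gave 39.7-39.8% at every exit share. Observed deaths still fell from 18.1 to 15.1, 13.2 and 11.2 at 30, 50 and 70% exit.

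**The case against.** A reader might infer that the OS curve is bound to be biased upward. The documents do not support that, for three reasons.

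- No section says OS will be censored at exit. The Kaplan-Meier sentence in section 8 follows the PFS design and does not mention OS.
- Direction depends on who leaves. Exit is triggered by needing systemic therapy or starting an agent. A progressor too ill for treatment may stay and have the death observed, while a fitter one leaves. The reverse is also possible, if those who stay have slow progression that needs no systemic therapy. The documents do not say which applies.
- Not every progressor leaves. Progression must require systemic therapy, mitotane is exempt, and repeat surgery is not listed as a trigger although section 1.2.5 says the site uses metastasectomy extensively.

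All three stand, and they limit the claim about size and direction. It is also fair that section 8 calls this a pilot and sets no OS test or benchmark, and that at 30% exit with leavers and stayers alike the error is smaller than the random error. Staff might learn of later deaths informally. None of this supplies the missing procedure: a patient who is off study has no planned contact.

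**Conclusion.** The gap is in the text and needs no assumption: OS is an objective, the two exit criteria stop the only planned contact, and no rule says how OS is analysed or censored. Followed as written, later deaths are not systematically observed.

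The size is conditional on censoring at exit and on the assumed exit share and survival after progression. The error is upward if leavers and stayers have similar survival after progression that is worse than before it. It is zero if the death hazard does not change at progression, and it can be slightly negative if leavers do much better than stayers. At 50% exit with leavers and stayers alike, it can be as large as the standard error.

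Deaths and precision are lost in every case. The harm is to a descriptive secondary estimate, so this is worth fixing but does not threaten the primary PFS test.

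**What to change.** - **Section 3.13.2:** state that these two criteria end protocol evaluation but not survival follow-up.
- **Section 3.11:** continue the existing six-monthly phone contact for these patients until death, withdrawal of consent, loss to follow-up or study closure. Record vital status, date of death and subsequent therapy.
- **Section 8:** define OS from a stated origin (for example the date of surgery and HIPEC), count all deaths whatever therapy came later, and censor only at the date last known alive.

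The cost is a protocol amendment, any consent change needed (the consent pages were not available to check), and about two calls per patient per year, so at most 2 × 30 = 60 calls a year. Treatment, sample size and the primary test do not change.
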